9.3. Vital Signs

Descriptive statistics of observed values will be presented for vital sign data by schedule study visit, including systolic blood pressure (mmHg), diastolic blood pressure (mmHg), oral temperature (C), heart rate (bpm) and respiration (breaths/minute) by treatment group for patients. Changes from baseline to each scheduled post-baseline visit will be presented.

Listings of individual vital sign data will be provided.

aTyr Pharma, Inc.
Study ATYR1923-C-002 Statistical Analysis Plan
IND#: 133692

FINAL Version 1.0
2021-08-02

9.4. 12-Lead ECG

PR interval, QRS duration, QTcF interval, QT interval and overall interpretation will be summarized in actual value and change from baseline by timepoint and treatment arm.

All 12-lead ECG data by patient will be presented in a listing.

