4. INVESTIGATIONAL PLAN

4.1. **Overall Study Design and Plan**

This randomized, double-blind, placebo-controlled, study will evaluate the safety, tolerability, immunogenicity, PK, and preliminary efficacy of multiple ascending doses of IV ATYR1923 in patients with pulmonary sarcoidosis undergoing a protocol-guided OCS tapering regimen.

This study will consist of 3 staggered multiple dose cohorts, as shown in Table 2.

	Dose		Dosing	
Cohort	(mg/kg)	# of Doses	Frequency	1

Planned Dose Cohorts

Cohort	Dose (mg/kg)	# of Doses	Dosing Frequency	N	Ratio ATYR1923: Placebo
1	1.0	6	Every 4 weeks	12	2:1
2	3.0	6	Every 4 weeks	12	2:1
3	5.0	6	Every 4 weeks	12	2:1

Each eligible patient will participate in only one cohort during the study. Within each cohort, 12 patients will be randomized 2:1 (block size of 6) to ATYR1923 (N=8) or placebo (N=4). Study drug will be administered via IV infusion every 4 weeks for a total of 6 doses (20 weeks of treatment). The follow-up study visit is scheduled for 4 weeks after the last infusion. The ATYR1923 doses levels to be evaluated are 1.0 mg/kg, 3.0 mg/kg, and 5.0 mg/kg. In total, approximately 36 patients with pulmonary sarcoidosis are planned to be randomized. The dose-escalation procedure is described in Section 7.1.3.1.

Day 1 is the calendar day of first infusion.

Starting on Day 15, patients will begin a taper (reduction) in OCS (per the ATYR1923-C-002 Oral Corticosteroid Taper Guidelines) from their starting dose of 10-25 mg/day of prednisone (or equivalent) to a target dose of 5 mg/day, to be completed on or before Day 50. The OCS dose will be tapered by 5.0 mg/day every 1 to 2 weeks, depending on the starting dose. Smaller incremental titrations to the target dose of 5 mg/day by Day 50 may be implemented per Investigator judgement. Patients will be maintained at the target dose of 5.0 mg/day (or equivalent) through Week 24/End-of-Study (EOS). Optionally, further titrations in the OCS dose to below 5 mg/day may be attempted after the Week 16 visit, if determined by the Investigator to be feasible.

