7. STUDY DRUG

7.1. Study Drug Dose and Administration

7.1.1. Treatments Administered

The planned study cohorts are identified in Table 2. In all study cohorts, it is planned that study drug will be administered as an IV infusion over approximately 60 minutes every 4 weeks for a total of 6 doses (20 weeks of treatment). Within each cohort, patients will be assigned to ATYR1923 or placebo according to the computer-generated randomization list (see Section 7.1.3).

Although this is an escalating dose study, if safety or tolerability issues are experienced, or the actual ATYR1923 PK appears to be substantially different from what is predicted, a different dose or interval may be administered in the next cohort. Further, an intermediate dose may be tested to gain more information on safety, tolerability and/or PK.

For the preparation of the ATYR1923 dose levels, the patient's weight at Screening will be used.

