8.5.2. Vital Signs and Temperature

Vital signs, including blood pressure, heart rate, and respiration rate, are to be measured at the time points designated in Table 1.

At each clinic visit, vital signs are to be measured before blood sample collection that day. Heart rate and blood pressure determinations will be measured after the patient has been lying supine for at least 5 minutes.

On study drug administration days, vital signs are to be measured pre-infusion and at 15 and 30 minutes (±5 minutes) and at 1, 2, and 4 hours (±15 minutes) after the start of infusion (SOI). Vital signs are to be measured before blood sample collection.

Temperature is to be measured at the time points designated in Table 1. On study drug administration days, temperature is to be measured pre-dose, 60 minutes (±15 minutes) after the SOI, and again at 4 hours (±15 minutes) after the SOI. Temperature is to be measured at the same time as vital signs.

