9.9.1. Anaphylaxis

IRRs meeting the definition of anaphylaxis are to be reported in the eCRF as such (Sampson et al. 2006):

1. Acute onset of an illness (minutes to several hours) with involvement of the skin, mucosal tissue, or both (eg, generalized hives, pruritus or flushing, swollen lipstongue-uvula).

And at least one of the following:

- a. Respiratory compromise (eg, dyspnea, wheeze-bronchospasm, stridor, reduced peak expiratory flow, hypoxemia).
- b. Reduced blood pressure or associated symptoms of end-organ dysfunction (eg, hypotonia [collapse], syncope, incontinence).
- 2. Two or more of the following that occur rapidly after exposure to a likely allergen for that patient (minutes to several hours):
 - a. Involvement of the skin-mucosal tissue (eg, generalized hives, itch-flush, swollen lips-tongue-uvula).
 - b. Respiratory compromise (eg, dyspnea, wheeze-bronchospasm, stridor, reduced peak expiratory flow, hypoxemia).
 - c. Reduced blood pressure or associated symptoms (eg, hypotonia [collapse], syncope, incontinence).
 - d. Persistent gastrointestinal symptoms (eg, crampy abdominal pain, vomiting).
- 3. Reduced blood pressure after exposure to known allergen for that patient (minutes to several hours):
 - a. Infants and children: low systolic blood pressure (age specific) or greater than 30% decrease in systolic blood pressure*.

b. Adults: systolic blood pressure of less than 90 mm Hg or greater than 30% decrease from that person's baseline.

Patients who experience anaphylaxis are to be managed as described in Section 9.9.

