10.1.2.3.3. Vital Signs, Pulse Oximetry and Electrocardiograms

Vital signs, pulse oximetry and ECG parameters will be listed and they will be presented descriptively, where applicable.

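### SAP 9.3 tabulates vital signs by visit only and the SAP plans no pulse oximetry summary, so no planned table compares the arms on the time course around the infusion

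*SAP*

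**What the plan says.** **Collection.** Protocol 8.5.2 sets six readings on each dosing day: "vital signs are to be measured pre-infusion and at 15 and 30 minutes (±5 minutes) and at 1, 2, and 4 hours" after the start of infusion. This covers blood pressure, heart rate and respiratory rate. Temperature has its own schedule of three: "temperature is to be measured pre-dose, 60 minutes (±15 minutes) after the SOI, and again at 4 hours (±15 minutes) after the SOI". Protocol 8.5.4 has pulse oximetry running continuously until the infusion ends and recorded at the vital-sign times. There are six infusions of about one hour each (protocol 4.1 and 7.1.1: "study drug will be administered as an IV infusion over approximately 60 minutes every 4 weeks for a total of 6 doses").

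**Planned analysis.** SAP 9.3 reads: "Descriptive statistics of observed values will be presented for vital sign data by schedule study visit". The parameters named are systolic and diastolic pressure, temperature, heart rate and respiration. Change from baseline is given for the scheduled visits that follow baseline, and individual vital signs are listed. For Day 1, SAP 7.3.1 fixes the baseline as the last reading before the first dose.

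**Pulse oximetry.** Protocol 10.1.2.3.3 says: "Vital signs, pulse oximetry and ECG parameters will be listed and they will be presented descriptively, where applicable". In the SAP, oximetry appears only in the copied schedule of events and its footnote. SAP section 9 has no summary of it, and SAP 3.3, which records changes from the protocol, does not mention it.

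**The concern.** The primary objective is the safety and tolerability of multiple ascending intravenous doses, and the serial readings are scheduled around each infusion. Protocol 9.9 treats infusion reactions as an expected risk of a biologic and names hypotension and hypoxia among the cardiorespiratory signs. A modest, dose-related dip in pressure or oxygen saturation during the infusion, too small for an investigator to call clinically significant, would be visible only if the readings were tabulated by time and arm. The plan as written has no such table. For oximetry it has no summary table at all, in patients whose disease is in the lung.

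**Working it through.** The plan states no figure to reproduce. The check is a count of scheduled readings, followed by a comparison of the SAP rules that might assign them to a table.

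**Inputs**
- Infusions per patient: 6 (protocol 4.1).
- Blood pressure, heart rate and respiratory rate: 6 readings per dosing day, 5 of them after the start (protocol 8.5.2).
- Oximetry: recorded at the same times (protocol 8.5.4).
- Temperature: 3 per dosing day, 2 of them after the start (protocol 8.5.2).
- Infusion length: about 60 minutes (protocol 7.1.1), so the 15-minute, 30-minute and 1-hour readings fall during the infusion or at its end.
- Planned patients: 36, with 24 on ATYR1923 and 12 on placebo (protocol section 5).

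**Counts, assuming all six infusions are given and every reading is taken**

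| Quantity | Arithmetic | Result |
|---|---|---|
| Dosing-day readings per patient, per parameter | 6 × 6 | 36 |
| of these, after start of infusion | 6 × 5 | 30 |
| of these, at 15 min, 30 min and 1 h | 6 × 3 | 18 |
| Temperature readings per patient | 6 × 3 | 18 |
| of these, after start of infusion | 6 × 2 | 12 |
| Post-start readings per parameter, all patients | 36 × 30 | 1,080 |
| on ATYR1923 / on placebo | 24 × 30 / 12 × 30 | 720 / 360 |
| Post-start Day 1 readings per parameter, all patients | 36 × 5 | 180 |

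**Where the SAP would put these readings**
1. SAP 9.3 gives one unit, the visit. It names no time within the visit and no rule for choosing or combining the readings.
2. SAP 7.3.1 recognises that Day 1 has several readings, but settles only which one is the baseline.
3. SAP 7.3.2 deals with unscheduled and repeated tests. The serial readings are scheduled, so it does not apply.
4. Day 1 is both the first infusion and the baseline visit. SAP 9.3 tabulates change only for later visits, so on a literal reading the five post-start Day 1 readings enter no change table.
5. At later visits, change is measured from the Day 1 pre-dose value. Any drift since Day 1 is then mixed with any acute effect of that day's infusion.
6. Oxygen saturation is not among the parameters of SAP 9.3 and is summarised nowhere else in SAP section 9.

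Whatever single value per visit a programmer chose (the pre-infusion reading, the last reading or some average), the table would not show the course from before the infusion to four hours after its start.

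**The case against.** The strongest reply is that infusion effects reach the safety tables by another route. Under protocol 8.5.7, clinically significant vital-sign and oximetry findings after dosing starts become adverse events. Events during or within 24 hours of an infusion are recorded as individual signs and symptoms. SAP 9.1 tabulates and lists suspected infusion-related events, and SAP section 8 shows each active arm separately beside combined placebo. SAP 7.3.3 promises listings of all collected data. SAP 7.4.1 allows descriptive categories to be expanded where useful. The DSMB reviews unblinded vital signs before escalation under its own charter, so escalation does not depend on SAP 9.3. The primary endpoint, incidence of TEAEs and SAEs, is unaffected.

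All of this stands, and it limits the point. It does not remove it. Adverse-event capture starts only at clinical significance, listings do not compare arms, and the expansion in SAP 7.4.1 is optional.

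The same material rules out several stronger readings that a reader might infer:
- **That the six readings are averaged into one visit value.** No such rule is stated. Any figure for how far a fall in pressure would be diluted would measure the reader's assumption.
- **That within-visit times were deliberately dropped because SAP 9.4 summarises ECG by timepoint.** The SAP uses the same word where it means the visit, for example for lung function in 11.1.1, so the difference in wording proves little.
- **That the safety tables show nothing of the infusion, or that oximetry is lost.** The infusion-related event table and the listings show otherwise.
- **That the blood-pressure figure in protocol 9.9.1 ("systolic blood pressure of less than 90 mm Hg or greater than 30% decrease from that person's baseline") is a ready-made outlier threshold.** It is one criterion in a definition of anaphylaxis, tied there to exposure to a known allergen.

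**Conclusion.** The point holds as a gap in summarisation. SAP 9.3 does not assign the serial dosing-day readings to any table row, its change tables literally pass over the post-start Day 1 readings, and the SAP omits a descriptive oximetry summary that the protocol leads one to expect, without recording the change. The words where applicable in protocol 10.1.2.3.3 leave some latitude, but oximetry is scheduled at every dosing visit, so a summary clearly applies.

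In size, 30 of 36 dosing-day readings per patient for each of blood pressure, heart rate and respiratory rate, and 12 of 18 for temperature, have no assigned place. The same 30 of 36 applies to recorded oxygen saturation, which has no summary at any time. These counts assume complete dosing and attendance. The consequence is that the planned tables cannot compare, by arm, the time course of vital signs or oxygen saturation around the infusion. No result or figure in the documents changes. This is a cheap improvement, not a flaw that threatens the primary analysis.

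**What to change.** In SAP 9.3:
- Summarise blood pressure, heart rate, respiratory rate, temperature and oxygen saturation by visit, nominal time point and arm, using each parameter's own schedule.
- Include Day 1.
- Present change from the same-day pre-infusion value alongside the planned change from baseline.
- Optionally add the lowest systolic pressure and lowest oxygen saturation per infusion, labelled as descriptive.

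If the sponsor prefers not to summarise oximetry, SAP 3.3 should record that as a departure from protocol 10.1.2.3.3 and give the reason.

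The cost is a few sentences of SAP text and a few more tables. The protocol already schedules the readings, so no visit or procedure changes.

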9.5. Physical Examinations

A by-patient listing will be generated to display all physical examination information, including abbreviated.

10. SECONDARY ENDPOINT ANALYSES

The following analyses will be performed using the mITT Set. OCS and PFT related analyses will also be presented using the EE Set.

10.1. Potential Decrease in Background Oral Corticosteroid Dose

For analyses in this section, the data will be summarized in different ways if there are missing data values for OCS dose. For details see Section 7.3.3.4.

10.1.1. OCS Data Sources

The sources of OCS use are summarized in the table below.

Time of Use	Data Source	CRF Name	Comments
Historical and current use at Screening	OCS LOG	OCS Log - Prior and Current Use table	Historical use will be added here. An additional row for every change in steroid or dose
Steroid use beginning on Day 1	eDiary	Patient Diary	Patients will be entering a form every day and from that data we can pull out any dosing changes or changes in use
	OCS LOG (for subjects who do not have eDiary)	OCS Log - Prior and Current Use table	Study Coordinators will be responsible for recording any dosing changes or changes in steroid use in this table based on the paper diaries completed by the subject

aTyr Pharma, Inc.
 Study ATYR1923-C-002 Statistical Analysis Plan
 IND#: 133692

FINAL Version 1.0
 2021-08-02

Changes in Dose	eDiary and OCS LOG for subjects without eDiary	Patient Diary and OCS Log - Prior and Current Use table	
-----------------	--	---	--

10.1.2. Steroid Dose Level Conversion

The dosage levels of OCS are collected as daily doses. For analysis purposes, the dose of any OCS other than prednisone or prednisolone will be converted to the prednisone equivalent dose using the following conversion factors:

Medication Term	Conversion factor
Prednisone	1
Prednisolone	1
Methylprednisolone	1.25
Triamcinolone	1.25
Dexamethasone	0.15
Betamethasone	0.12

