7.1.6. Concomitant Medication and Other Restrictions During the Study

7.1.6.1. Prohibited or Restricted Concomitant Medications and Substances

The following treatments and procedures are prohibited prior to and/or during study participation, as indicated below:

- Immunomodulatory agents, such as TNF-α inhibitors (eg, infliximab, adalimumab), are prohibited from 4 months of Day 1 and through the duration of study drug treatment.
- Live vaccination within 8 weeks before Day 1 and during study participation is prohibited.
- All investigational agents or devices (other than ATYR1923) within 3 months for small molecules and 6 months for biologics, or 5 half-lives (if known) of the agent, whichever is longer, before the first study drug dose and through the duration of study drug treatment.
- Major surgeries are prohibited from 3 months before the first study drug dose through the duration of study drug treatment.

- Heavy smoking/inhalation of tobacco/nicotine-containing products >20 cigarettes/day or e-cigarette equivalent.
- Topical treatment of any lesion identified by the Investigator for cutaneous assessments (eg, biopsy).

All other concomitant medications and procedures are allowed.

Concomitant medications are to be recorded in the source documents and in the eCRF.

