7.3.3.4. Imputation Methods for Missing OCS Dose Data

OCS dosage levels will not be imputed, and those that are recorded as "ongoing" or are missing an end date in the collected OCS information will be assumed to have been taken up to the date of last visit. The data listings will not show an end date.

aTyr Pharma, Inc.
 Study ATYR1923-C-002 Statistical Analysis Plan
 IND#: 133692

FINAL Version 1.0
 2021-08-02

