8.3. Demographics and Baseline Characteristics

Patient demographic data as taken at screening, including age (continuous and categorical 18-64 and 65+), sex, ethnicity, and race will be summarized.

Baseline characteristics as collected on Day 1, including weight (kg), height (cm), BMI (kg/m^2), Baseline Dyspnea Index total score, Baseline Modified MRC Dyspnea scale score, key lung function variables, Sarcoidosis diagnosis at screening (all organ systems involved), and duration of disease will be summarized.

Also to be summarized are anti-sarcoidosis treatment at baseline (refer to Section 7.3.1 for baseline definition) including OCS type and dose categories (10 mg/day to <15 mg/day, 15 mg/day to <20 mg/day and 20 mg/day or higher), oral immunomodulator type at the time of baseline using the same baseline definition.

The demographic data and baseline characteristics will be summarized for the Safety, mITT and EE Sets. If they are the same, only mITT tables are needed.

aTyr Pharma, Inc.
Study ATYR1923-C-002 Statistical Analysis Plan
IND#: 133692

FINAL Version 1.0
2021-08-02

A patient's age in years is calculated as (date of screening - date of birth)/365.25. BMI is calculated by dividing the weight of patient screening in kg by the square of their height in meters.

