10.1.4. Study Drug Adjusted OCS Burden

Since a missed dose in study treatment is likely to affect OCS dose, in order to isolate the effect of treatment, the above mentioned OCS dose, change from baseline and percent change from baseline analyses will be repeated, but excluding a window around a missed dose of study treatment, where a window is defined as 30 days after the previous dose and restart on the day of the next administered dose. Active treatment and placebo will be compared in the same way as in time adjusted OCS burden in the previous section.

10.1.5. Achievement of Target Taper Dose of Prednisone 5 mg/day (or Equivalent) and Maintained Through Week 24

The number and percentage of patients who have achieved the following will be summarized.

1. **Ability to Taper:** Taper OCS dose level down to 5mg/day or less at any time and remained for at least 5 consecutive days.
2. **Maintain Taper:**
 - a. Taper OCS dose level down to 5mg/day or less at any time and remained for at least 30 consecutive days.
 - b. Taper OCS dose level down to 5mg/day or less at any time and remained for at least 60 consecutive days.
 - c. Taper OCS dose level down to 5mg/day or less at any time and remained for at least 90 consecutive days.
 - d. Taper OCS dose level down to 5mg/day or less at any time and remained for at least 115 consecutive days

- e. Time to first relapse of taper for sarcoidosis. Defined as the duration from the first day of hitting 5mg (plus 5 consecutive days) to when >5mg is needed. If the reason for increase in OCS is unrelated to sarcoidosis (as identified from the eCRF) then that episode will not count as a relapse and counting of the duration will recommence on the next day on which 5mg is achieved. For patients who maintain 5mg after successful taper will be censored at 30 days after last dose or EOS (if earlier). Patients who never reach 5 mg will be assigned a duration of 1 day and be classified as a censored data point.
- f. Proportion of days at 5mg or less ignoring diary days when OCS dose was increased >5mg for non-sarcoidosis events (i.e. same exclusion as the Time to First Relapse endpoint)
- g. Proportion of days at 5mg or less including all diary days (i.e. even those when OCS dose was increased >5mg for non-sarcoidosis events)

In each of the above endpoints, when study drug dosing is missed, OCS diary data >30 days after previous study drug infusion will be ignored until dosing restarted as described in Section 10.1.4.

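### SAP 10.1.2 states no operation for conversion factors that lie on both sides of 1; multiplied, dexamethasone and betamethasone count as about 7 and 8 times weaker than prednisone, apparently an inverted scale

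*SAP*

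**What the plan says.** SAP 10.1.2 collects oral corticosteroid (OCS) as daily doses and states that, for analysis, "the dose of any OCS other than prednisone or prednisolone will be converted to the prednisone equivalent dose using the following conversion factors". The table gives:

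- prednisone and prednisolone: 1
- methylprednisolone and triamcinolone: 1.25
- dexamethasone: 0.15 ("Dexamethasone 0.15")
- betamethasone: 0.12

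The section gives no operation, worked example or equivalence reference. Nothing elsewhere fills the gap. SAP 10.1.3 describes the quantity entering the time-adjusted AUC only as an OCS dose in mg, and the protocol speaks only of prednisone or its equivalent.

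Several analyses use OCS doses:

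- the time-adjusted AUC and its baseline OCS covariate (SAP 10.1.3), repeated with missed-dose windows removed (10.1.4)
- the 5 mg/day taper items (10.1.5)
- the baseline OCS dose categories (8.3)

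Two of the taper items treat steroid given for other reasons differently. For time to first relapse (item 2e), "If the reason for increase in OCS is unrelated to sarcoidosis (as identified from the eCRF) then that episode will not count" as a relapse. Item 2g instead takes the "Proportion of days at 5mg or less including all diary days".

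**The concern.** A conversion column should run in one direction. Here two drugs have factors above 1 and two have factors well below 1, so whichever operation the programmer picks, the two pairs fall on opposite sides of prednisone. That suggests the first pair is written as mg prednisone per mg drug and the second pair the other way round.

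Steroid sparing is the first-listed secondary objective, and the converted dose carries it. If doses are multiplied, a day on dexamethasone or betamethasone alone can pass as a day at or below 5 mg and adds too little to the AUC. The taper items at 5, 30, 60, 90 and 115 consecutive days (items 1 and 2a to 2d) and item 2g are not limited to sarcoidosis-related use, so they are exposed whatever the drug was given for. A missed relapse under item 2e is narrower: the drug would have to replace prednisone and be given for sarcoidosis.

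**Working it through.** **Inputs.** The factors come from SAP 10.1.2 and the 5 mg/day limit from SAP 10.1.5. The AUC window comes from SAP 10.1.3 and the visit schedule, and the planned 8 active patients per cohort from SAP 5.1. The SAP gives no worked conversion to reproduce.

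**Both readings.** With factor f, 1 mg of drug becomes f mg prednisone if multiplied and 1/f if divided. The two readings differ by f² or 1/f², whichever exceeds 1.

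| Drug | f | Multiply | Divide | Gap between readings |
|---|---|---|---|---|
| Methylprednisolone, triamcinolone | 1.25 | 1.25 | 0.80 | 1.25² = 1.56 |
| Dexamethasone | 0.15 | 0.15 | 6.67 | 1/0.15² = 44.4 |
| Betamethasone | 0.12 | 0.12 | 8.33 | 1/0.12² = 69.4 |

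Neither column puts all four drugs on the same side of 1.

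**The 5 mg/day limit, multiplied.** The largest dose that still passes when taken alone is 5/f:

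- dexamethasone: 5/0.15 = 33.3 mg/day
- betamethasone: 5/0.12 = 41.7 mg/day

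If the drug is added to 5 mg prednisone and the doses are summed, the day is 5 + f·d, which exceeds 5 for any d > 0. The misclassification therefore needs the drug to be taken in place of prednisone.

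**Size of the understatement, multiplied.** The documents give no potencies, so I use a range. The lower end assumes each drug merely equals prednisone per mg: 1/0.15 = 6.7-fold and 1/0.12 = 8.3-fold. The upper end assumes the table's reciprocals are right: 44-fold and 69-fold.

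**Effect on the AUC.** The later window starts on Day 51. On schedule, the last infusion is Day 141 and 30 days after it is Day 171, but end of study is Day 169, so N − M = 169 − 51 = 118 days. In the trapezoid sum each interior day has weight 1. For 1 mg/day taken alone on 10 interior days, the patient's time-adjusted AUC is understated by:

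- dexamethasone: (1 − 0.15) × 10/118 = 0.072 to (6.667 − 0.15) × 10/118 = 0.552 mg/day
- betamethasone: (1 − 0.12) × 10/118 = 0.075 to (8.333 − 0.12) × 10/118 = 0.696 mg/day

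Divided by 8, one such patient moves an active arm's mean by 0.009 to 0.069 mg/day (dexamethasone) or 0.009 to 0.087 mg/day (betamethasone). All of these scale linearly with dose and days.

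**Methylprednisolone.** This is the one alternative the protocol names (inclusion criterion 4), and here the missing operation is what matters. It meets the 5 mg/day limit up to 5/1.25 = 4 mg/day if multiplied, but up to 5 × 1.25 = 6.25 mg/day if divided. Doses above 4 and up to 6.25 mg/day are therefore classified oppositely. A baseline dose of 8 mg/day is 8 × 1.25 = 10 mg if multiplied and 8/1.25 = 6.4 mg if divided; the latter falls below the lowest baseline category in SAP 8.3.

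**The case against.** The strongest reply is that inversion cannot be proved from the documents, because neither gives any potency. That stands, and it is why the point rests on a stated assumption. The assumption concerns only direction, that each drug is at least as strong per mg as prednisone. If it fails for dexamethasone and betamethasone, the defect reduces to the unstated operation. That alone would be a smaller matter, since multiplying is the ordinary reading and leaves methylprednisolone unaffected.

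Second, no use of dexamethasone or betamethasone is shown. This also stands. After its list of prohibitions, which names neither drug, protocol 7.1.6.1 says "All other concomitant medications and procedures are allowed", but that shows permission rather than use. SAP 10.1.1 asks for "An additional row for every change in steroid or dose" in the row for use up to Screening, and its on-study rows also provide for changes in steroid use. A switch is therefore foreseen, though not necessarily to these drugs.

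Third, the SAP does not say outright that the baseline covariate and baseline categories use converted doses; SAP 7.3.1 takes the baseline dose from the log. The stated analysis purpose of 10.1.2 makes that the reasonable reading, but it is an inference. A multiplied baseline error would probably also be noticed: any dexamethasone dose below 10/0.15 = 66.7 mg/day would fall outside every category in 8.3. That safeguard does not cover on-study days.

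Finally, the shifts are illustrative and dilute in the pooled comparison. With 24 combined active patients the upper figures become 0.552/24 = 0.023 and 0.696/24 = 0.029 mg/day; with 12 combined placebo patients, 0.046 and 0.058. The SAP plans no formal hypothesis testing, and the primary endpoint is safety. These points limit the weight of the concern but do not make the table usable as it stands.

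**Conclusion.** The concern holds. From the documents alone, the conversion has no stated operation, and its factors cannot all sit on the same side of prednisone under either operation. If each listed drug is at least as strong per mg as prednisone, the dexamethasone and betamethasone entries are on the inverse scale and the table gives wrong converted doses as written. Dividing throughout only moves the error to methylprednisolone and triamcinolone.

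The error per affected dose is large, but its effect on the trial's results is unknown and may be nil, because it depends on use that the documents do not report. The point should be fixed, with medium confidence. It does not touch the primary safety analysis.

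**What to change.** In SAP 10.1.2:

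1. State that the recorded daily dose is multiplied by the factor, and define the factor as mg prednisone per mg of drug for every row.
2. Cite an equivalence reference and check each entry against it before unblinding. If the dexamethasone and betamethasone entries are confirmed as inverted, replace them with their reciprocals, 1/0.15 = 6.67 and 1/0.12 = 8.33.
3. Say explicitly that the AUC, the baseline OCS value and categories, and the 5 mg/day items all use the converted dose.

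This changes the analysis conversion only, not how any patient is dosed. The cost is a sentence or two, one reference, at most two table entries and one lookup in the programs. No new data are needed.
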